### METHODS

**Overview:** A randomized, double-blind, placebo-controlled clinical trial among individuals (N=90) with SUD and PTSD will be conducted to test the hypothesis that N-acetylcysteine (NAC) will significantly reduce SUD severity, craving, and PTSD symptoms. A subset of enrolled subjects between the ages of 21-40 will complete neuroimaging procedures before and after treatment. All procedures will be reviewed by the MUSC IRB and the Ralph H. Johnson VA Research and Development committee prior to study start.

**Participants:** Ninety male and female participants between the ages of 18 to 75 with current AUD/SUD and comorbid PTSD or sub-threshold PTSD will be recruited to participate in the study.

**Recruitment:** Primary recruitment sites include (1) the Ralph H. Johnson VAMC outpatient Substance Treatment and Recovery Clinic (STAR) and (2) the PTSD Clinical Team (PCT).

**Inclusion/Exclusion Criteria:** To be included, subjects must (1) be 18-75 years old, (2) meet DSM-5 criteria for current PTSD or subthreshold PTSD, and (3) meet DSM-5 criteria for current AUD/SUD. Exclusion criteria include: (1) schizophrenia, bipolar disorder or an eating disorder; (2) any significant medical illness (e.g., asthma) that may adversely affect safety or study participation; (3) psychotropic medication initiation within 4 weeks of study participation or use of the following medications: carbamazepine, phenytoin, nitrous oxide, methotrexate, 6-azauridine triacetate, nitroglycerin or any other medication that may have an adverse interaction with NAC; (4) pregnant or nursing women; and (5) clinically significant suicidal ideation and intent.

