## Protocol: Glial Regulators for Testing Comorbid Posttraumatic Stress Disorder and Substance Use Disorders

total number of standard drinks consumed and the OCDS total score as the primary outcomes. A Poisson distribution will be assumed with a logarithm link function to assess the effects of NAC treatment. Data collected in substance abuse studies often contain a preponderance of zeros, and these zeros in the distribution can be considered sampling zeros in the Poisson process (Bandyopadhyay et al., 2011). If this excess is present in the distribution, two-part Hurdle models (Poisson and NB) will be explored (Cragg et al., 1971). The hurdle part of the model will allow us to estimate the probability of abstinence during the study period (as an odds ratio) while the Poisson/NB portion will allow for the assessment of the risk of an increase in using days beyond zero during the study period (as a risk ratio). Baseline alcohol/substance use and craving will be included in pertinent models as covariates. Additional alcohol/substance use outcomes will be assessed: change in percent drinking days, percent heavy drinking days, EtG, and VAS craving levels.

Hypothesis 2: NAC treatment will result in significantly greater reduction in PTSD severity (CAPS-5) as compared to placebo. To test this hypothesis, generalized linear mixed effects regression models with a Gaussian distribution will be developed to assess group differences while adjusting for baseline CAPS-5 scores. Assumptions of residual normality and homoscedasticity will be checked using statistical test and graphical methods (Residual and Q-Q plots, and Shapiro-Wilk tests) and transformation will be done as necessary. Restricted maximum likelihood methods will be used to estimate the fixed effects and variance components. Additional outcomes (e.g., PCL-5, CAPS-5 symptom subscales) will be examined.

Hypothesis 3A: Prefrontal cortex-amygdala connectivity at rest and in response to alcohol/drug vs. neutral cues will predict reduction in alcohol/substance use severity (total standard drinks).

Hypothesis 3B: Prefrontal cortex-amygdala connectivity at rest and in response to trauma vs. neutral cues will predict reduction in PTSD severity (CAPS-5).

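### With excess zeros, the plan's only described drinking analysis is a hurdle model: no part is named as the H1 test, and the count part covers drinkers only and is worded in days

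*Combined protocol and SAP*

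**What the plan says.** The statistical section for Hypothesis 1 sets up a mixed-effects model with "total number of standard drinks consumed and the OCDS total score as the primary outcomes". The default is stated next: "A Poisson distribution will be assumed with a logarithm link function to assess the effects of NAC treatment". The plan then remarks that "Data collected in substance abuse studies often contain a preponderance of zeros" and continues: "If this excess is present in the distribution, two-part Hurdle models (Poisson and NB) will be explored". No threshold for excess is given.

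The two parts are then described. The hurdle part estimates the probability of abstinence over the study, as an odds ratio. The other part is described as follows: "the Poisson/NB portion will allow for the assessment of the risk of an increase in using days beyond zero during the study period". It is to be reported as a risk ratio. Baseline use and craving enter the relevant models as covariates. Percent drinking days is listed at the end of the same paragraph as an additional outcome.

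Two other places bear on this. The description of the Timeline Follow-Back lists total standard drink units and percent of days using as separate examples of what the instrument yields. Under Inclusion/Exclusion Criteria, participants must "meet DSM-5 criteria for current AUD/SUD", so a person with a drug use disorder and no alcohol use disorder can enrol and may record no drinks at all.

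**The concern.** The plan itself expects many zeros, and eligibility adds to them, so the branch for excess zeros may well be used. On that branch three things are unsettled or inconsistent.

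1. **No test is named.** The hurdle model yields two treatment effects. The plan does not say which decides Hypothesis 1, how they combine, or whether a contrast in drinks over all participants is kept.
2. **The count part is not a randomised comparison.** Abstinence during treatment is an outcome that NAC may change. Restricting to values above zero compares NAC participants who still drink with placebo participants who still drink. If NAC moves lighter drinkers to abstinence, those left on NAC are heavier on average.
3. **The unit does not match.** The outcome is standard drinks; the count part is worded in using days.

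At stake is the reading of a primary result. A ratio above 1 among drinkers could be taken as harm when nobody drank more, and the two parts could disagree with no rule for resolving it.

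**Working it through.** The plan gives no abstinence rate, drinking distribution or expected count ratio, so it has no figure of its own to reproduce here. Its sample size of 58 for AUD/SUD severity is not an input. All rates below are assumptions chosen to show direction and range.

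**Step 1. Two-group arithmetic.** Assume half are light drinkers (40 drinks if they drink) and half heavy (200). Abstinence in light/heavy drinkers is 30%/10% on placebo and 60%/10% on NAC. Nobody drinks more on NAC.
- Placebo: light drinkers still drinking 0.5 × 0.7 = 0.35; heavy 0.5 × 0.9 = 0.45. Mean over everyone 0.35 × 40 + 0.45 × 200 = 104. Mean among drinkers 104 / 0.80 = 130.0.
- NAC: light 0.20, heavy 0.45. Mean over everyone 0.20 × 40 + 0.45 × 200 = 98. Mean among drinkers 98 / 0.65 = 150.8.
- Count ratio 150.8 / 130.0 = 1.16. All-randomised ratio 98 / 104 = 0.94. Abstinence odds ratio (0.35/0.65) / (0.20/0.80) = 2.15.

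Here the count ratio stays above 1 unless NAC also cuts drinking among drinkers by about 14% (130.0 / 150.8 = 0.86).

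Other light/heavy means with the same abstinence rates:

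| Light/heavy drinks | Count ratio | All-randomised ratio |
|---|---|---|
| 80/120 | 1.05 | 0.85 |
| 60/150 | 1.11 | 0.90 |
| 40/200 | 1.16 | 0.94 |
| 20/200 | 1.19 | 0.97 |

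If abstinence instead rises from 20% to 40% in both groups, the count ratio is 1.00 and the all-randomised ratio 0.60/0.80 = 0.75. There is then no reversal.

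**Step 2. Continuous drinking amounts.** Assume abstinence of 20% on placebo and 40% on NAC, so a quarter of would-be drinkers (0.20/0.80) become abstinent. Amounts are gamma with mean 1. The all-randomised ratio is 0.75 × the count ratio.
- Exactly the lightest quarter quit. For shape 1 the cut-off is −ln 0.75 = 0.288 and the mean above it 1.288: count ratio 1.29, overall 0.97. For shape 0.5: 1.32 and 0.99.
- The chance of quitting only declines with amount, in proportion to exp(−y). For shape 1 it is 0.5·exp(−y), and the count ratio is (1 − 0.125)/0.75 = 1.17, overall 0.875. For shape 0.5: 1.22 and 0.92.

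**Step 3. With baseline adjustment.** Steps 1 and 2 are unadjusted. A zero-truncated negative binomial count part adjusted for baseline was simulated, with unmeasured severity driving both abstinence and amount.
- No effect on amount: count ratio about 1.11 (abstinence log odds ratio 1.0) and 1.20 (log odds ratio 1.5), against all-randomised ratios of about 0.82 and 0.72. At N = 90 the count ratio exceeded 1 in 63–69% of trials.
- A true 10% cut in every drinker: count ratios 1.01 and 1.06.
- No unmeasured link: about 1.0.

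**Step 4. Days against drinks.** 25 days at 6 drinks against 25 days at 4 gives a days ratio of 1.00 and a drinks ratio of 100/150 = 0.67. If the second group has 28 days at 4, the ratios are 28/25 = 1.12 and 112/150 = 0.75. The two measures can disagree even in direction.

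**Step 5. What an overall-mean test costs.** Take 45 per arm (1:1 assumed), two-sided 0.05, unadjusted, under Step 2. The abstinence comparison of 40% with 20% has z = 0.20 / √(0.24/45 + 0.16/45) = 2.12, so power is about 55%. The overall mean ratio of 0.875–0.99 has power of about 5–8%. The count part would be significant in the direction of harm in roughly 9–20% of trials.

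**The case against.** **The plan does not announce a switch of test.** It says that "two-part Hurdle models (Poisson and NB) will be explored", and the Poisson model remains the stated default. A reader might infer that the hurdle model becomes the H1 test; the text does not say so. This stands. What remains is that the role of the two parts is undefined on the only branch described for excess zeros.

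**The abstinence part is sound.** A reader might infer that neither part answers Hypothesis 1. That is too strong. The hypothesis is worded as severity, abstinence is listed among the Timeline Follow-Back measures, and the odds ratio keeps everyone randomised. It does not measure total drinks, but only the count part has the selection problem.

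**The largest ratio is an extreme.** A spurious 30% increase requires quitting by exactly the lightest quarter, no effect on anyone else and no adjustment. The plan does adjust for baseline use and craving. This stands, and 1.3 is not an expectation. Adjustment, however, removes the selection only as far as those measures explain who becomes abstinent.

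**Two chances at significance.** The plan does not say that either part counts as success at 0.05, so this would be an inference from silence.

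**An overall-mean test is weak where abstinence is the whole effect.** Step 5 confirms it. Preferring the overall mean is partly a choice of target; its justification is that total drinks is the outcome the plan names.

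**Conclusion.** The concern holds in limited form. Two parts rest on the wording alone: no test of Hypothesis 1 is specified once zeros are in excess, and using days must be reconciled with standard drinks. The third follows from how a hurdle model works: its count part conditions on a post-randomisation outcome.

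The size rests on assumed abstinence rates and drinking distributions. With selective quitting by lighter drinkers, a count ratio of about 1.1–1.2 is plausible, and about 1.3 is the extreme unadjusted case. Without such selection it is about 1.0. The documents therefore do not support a prediction that the result will reverse; they leave it possible and provide no named contrast to settle it. This should be corrected before analysis, but it does not undermine the design.

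**What to change.** In the Hypothesis 1 analysis, state that the drinking test is the NAC/placebo ratio of mean total standard drinks in all randomised participants, zeros included, whether or not zeros are in excess. Keep the planned log-link mixed-model framework with baseline drinking as covariate, and allow for overdispersion. A negative binomial model, robust standard errors or a marginalised hurdle model would each serve; the trial team can choose, provided the choice is fixed before unblinding.

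Report the abstinence odds ratio as a randomised supportive result. Restate the count part in standard drinks, and label it as conditional on drinking and not a randomised comparison.

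The cost is SAP wording and one additional model run. The real downside is low power in the overall mean for an effect confined to abstinence, especially among light drinkers. The odds ratio should therefore be reported prominently beside the main result. If the team regards abstinence as the main target, it should say so in advance and name that as the test.

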**Table 1. Assessment Instruments and Timeline**

Instrument	Baseline	Medication Initiation	Medication and Symptom Monitoring								Follow Up
	Weeks → -1	0	1	2	3	4	5	6	7	8	1 & 3 Mth
Demographic Data	X										
History and Physical Examination	X										
MINI Diagnostic Interviews	X										
Concurrent Medications Form	X	X	X	X	X	X	X	X	X	X	X
Vital Signs	X					X				X	
Medication Log		X	X	X	X	X	X	X	X	X	
Urine Pregnancy Test for Females	X					X				X	
Urine Drug Screen: UDS	X					X				X	X
Riboflavin Test		X				X				X	
Adverse Events		X	X	X	X	X	X	X	X	X	X
Breathalyzer/Saliva BAC Tests	X	X	X	X	X	X	X	X	X	X	X
Timeline Follow- Back: TLFB	X	X	X	X	X	X	X	X	X	X	X
CIWA-AR	X										
Visual Analog Scales; VAS	X	X	X	X	X	X	X	X	X	X	X
Obsessive Compulsive Drinking Scale: OCDS	X	X	X	X	X	X	X	X	X	X	X
Ethyl glucuronide (EtG)		X				X				X	X
Clinician Administered PTSD Scale: CAPS-5	X					X				X	X
PTSD Checklist: PCL-5	X		X	X	X	X	X	X	X	X	X
Life Events Checklist: LEC-5	X										
Childhood Trauma Questionnaire: CTQ-SF	X										
Beck Depression Inventory-II: BDI-II	X		X	X	X	X	X	X	X	X	X
Deployment Risk & Resiliency Inventory-2	X										
Columbia Suicide Severity Rating Scale	X					X				X	X
Penetration of the Blind Questionnaire										X	
AUDIT	X										
Cognitive Testing		X				X				X	
Blame Questionnaire	X									X	
Fagerstrom	X										
Coping Inventory	X									X	
Visual Analog Scale: VAS - fMRI	X									X	
History of Head Injuries BL	X										
History of Head Injuries FU										X	
Satisfaction Questionnaire										X	X
Treatment Services Review	X	X	X	X	X	X	X	X	X	X	X
Neuroimaging Procedures	■										■
Cognitive Behavioral Therapy: CBT			◆	◆	◆	◆	◆	◆	◆	◆	

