### **Trauma History and PTSD**

- Clinician Administered PTSD Scale (CAPS) (Weathers, Keane, & Davidson, 2001): The CAPS for DSM-5 is a 30-item structured diagnostic interview and gold standard for assessing PTSD (Weathers et al., 2014). The CAPS has excellent psychometric properties and diagnostic efficiency (Weathers et al., 2001). The CAPS-5 was revised to accommodate changes made in DSM-5, reduce administration time, and facilitate scoring procedures.
- PTSD Checklist (PCL-5) (Weathers et al., 2013): The PCL-5 is a 20-item self-report measure. The PCL-5 is similar in form to the PTSD Checklist (PCL) based on the DSM-5 (Weathers et al., 1993), which has excellent psychometric characteristics for screening and as a secondary indicator of PTSD symptom severity (McDonald & Calhoun, 2010).
- Life Events Checklist for DSM-5 (LEC-5) (Weathers et al., 2013): The LEC-5 assesses lifetime exposure to trauma. It includes the list of 16 different events from the original LEC. In addition, two items screen for military sexual trauma. The primary addition to the LEC-5 is a category involving occupational exposure (e.g., paramedic, police, or other first responder).
- Childhood Trauma Questionnaire-Short Form (CTQ-SF) (Bernstein et al., 2003): The CTQ is a 28-item self-administered inventory that assesses childhood abuse and neglect. The CTQ-SF contains subscales including physical, sexual, and emotional abuse, and physical and emotional neglect.

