## Protocol: Glial Regulators for Testing Comorbid Posttraumatic Stress Disorder and Substance Use Disorders

Following auto-shimming, single-voxel water-suppressed  $^1\text{H}$ -MRS spectra will be acquired using a Point Resolved Spectroscopy (PRESS) sequence: Repetition Time (RT) = 2000ms; Echo Time (TE) = 40ms; number of averages = 128; an unsuppressed water spectrum will be co-acquired (TE = 40ms, number of averages = 16), scaled for partial volume effects and relaxation, and used as a concentration reference (Mullins et al., 2008).

Participants will be asked to relax and keep their eyes opened and fixed on a cross-hair for two six-minute runs while resting state data are collected. Following this, participants will be exposed to alcohol/drug, trauma and neutral cues, which will be audio recorded descriptions of the most recent time they used alcohol/drug, details of a traumatic event, and details about a relaxing event.

We will use a block design consisting of a single run in which 4 task blocks alternate with rest blocks. The 4 task blocks consist of a neutral cue followed by a trauma cue followed by a neutral cue then an alcohol/drug cue. To minimize potential carry-over effects, the order of task blocks will be counterbalanced so that half of the subjects in the placebo group and half of the subjects in the NAC group are exposed to the alcohol/drug cue first and the remaining participants in each group are exposed to the trauma cue first. This order will be repeated at the end of treatment scan. T2\*-weighted gradient-echo planar images (EPI) will be acquired with the following parameters: TR = 1100ms, TE = 30ms, flip angle =  $65^\circ$ , matrix 64 x 64, field of view = 192mm, slice thickness = 3.0mm, with 48 slices to cover the entire brain.

**Statistical Analyses:** Baseline clinical and demographic characteristics will be collected and contrasts performed between treatment groups. Baseline characteristics found to be significantly associated with primary outcome measures will be included as covariates in the analyses. In general, less than 10% missing data have little impact on power and do not introduce bias, regardless of the missing data mechanism. If the percent missing data are greater than 10%, propensity score methods will be used for data imputation.

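### The Hypothesis 2 analysis does not use the weekly PCL-5 to inform missing CAPS-5, and the imputation rule for more than 10% missing names no predictors

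*Combined protocol and SAP*

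**What the plan says.** Under Statistical Analyses, Hypothesis 2 is that "NAC treatment will result in significantly greater reduction in PTSD severity (CAPS-5) as compared to placebo". The model is described as follows: "generalized linear mixed effects regression models with a Gaussian distribution will be developed to assess group differences while adjusting for baseline CAPS-5 scores", fitted by restricted maximum likelihood. PCL-5 enters that paragraph only at its end: "Additional outcomes (e.g., PCL-5, CAPS-5 symptom subscales) will be examined".

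Table 1 gives the schedule. The row "Clinician Administered PTSD Scale: CAPS-5" is marked at baseline, week 4, week 8 and the 1- and 3-month follow-ups. The row "PTSD Checklist: PCL-5" is marked at baseline, at each of weeks 1 to 8 and at follow-up. The section on Trauma History and PTSD describes the checklist as useful "as a secondary indicator of PTSD symptom severity".

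The only missing-data text opens the Statistical Analyses section. It states that "less than 10% missing data have little impact on power and do not introduce bias, regardless of the missing data mechanism". It then adds: "If the percent missing data are greater than 10%, propensity score methods will be used for data imputation". It does not say which variables enter the propensity model, what the percentage is taken over, or how the imputed values combine with the mixed model. No CAPS-5 assessment at early termination is described.

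**The concern.** A mixed model fitted to CAPS-5 alone assumes that dropout depends only on arm, baseline CAPS-5 and the on-treatment CAPS-5 values already seen. For someone lost in weeks 1–3 there are no such on-treatment values. For someone lost in weeks 5–7 the latest is from week 4. If people leave because symptoms have just worsened, the information that explains their leaving is in the weekly PCL-5, which this model does not see.

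At stake is bias in the week-8 NAC–placebo difference, mainly when the link between symptoms and leaving differs by arm. If worsening participants leave placebo, the placebo mean looks too good and the effect is understated. If the same happens on NAC, the error runs the other way. A separate PCL-5 analysis does not repair the CAPS-5 estimate.

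**Working it through.** **No plan figure to reproduce.** The documents give no dropout rate, no CAPS-5/PCL-5 correlation and no allocation ratio. The sample-size figures play no part here. N = 90 is from the Overview; everything else below is an assumption.

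**Step 1: data available to each analysis** (from Table 1, with baseline CAPS-5 as covariate)

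| Participant lost to all later assessments | On-treatment CAPS-5 | Weekly PCL-5 |
|---|---|---|
| before week 4 | 0 of 2 | up to 3 |
| between weeks 4 and 8 | 1 of 2 | 4 to 7 |

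**Step 2: how many people.** With constant weekly dropout reaching a total D by week 8, the share lost before the week-4 visit is 1 − (1 − D)^(4/8).

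| D | No on-treatment CAPS-5: 90 × [1 − √(1 − D)] | Week 4 only: 90 × D minus the previous column |
|---|---|---|
| 10% | 4.6 | 9 − 4.6 = 4.4 |
| 20% | 9.5 | 18 − 9.5 = 8.5 |
| 35% | 17.4 | 31.5 − 17.4 = 14.1 |

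**Step 3: bias of a CAPS-5-only likelihood analysis.** The simulations used a latent severity course, weekly PCL-5, CAPS-5 at weeks 0, 4 and 8, and monotone dropout. Each outcome was regressed on arm, baseline and earlier outcomes among those still present, and the arm coefficients were chained; this is equivalent to maximum likelihood under monotone dropout. Understatement = 1 − estimate/true effect. Unless noted, the true effect is 0.40 SD, the correlation is 0.75 and dropout depends on recorded PCL-5.

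| Dropout mechanism | Dropout, placebo/NAC | CAPS-5 only | With weekly PCL-5 |
|---|---|---|---|
| Unrelated to symptoms | – | none | none |
| Same in both arms | about 10% | under 1% | – |
| Same in both arms | 39%/32% | 4% | 0% |
| Symptom-driven on placebo only | about 10%/9% | 5% | within about 1.3% |
| Symptom-driven on placebo only | 19%/14% | 11% | within about 1.3% |
| Symptom-driven on placebo only | 42%/25% | 24% | within about 1.3% |
| Symptom-driven on placebo only | 46%/26% | 18–20% | about 1% |

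In the last row the estimate was 0.33 SD: 1 − 0.33/0.40 = 17.5%, or 1 − 0.33/0.41 = 20% against the comparison value in those runs.

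A deliberately adverse variant made dropout follow PCL-5 in opposite directions in the two arms (correlation 0.6 or 0.8; true effect 0.387 or 0.447 SD). The understatement was 5–12% at 10% dropout, 11–25% at 20% and 16–41% at 35%. For example, 1 − 0.366/0.387 = 5% and 1 − 0.230/0.387 = 41%. With PCL-5 the estimate was within about 3% of the truth.

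**Step 4: dropout that follows unrecorded severity.** With placebo-only dropout of about 35% driven by current, unobserved severity, the bias fell from 22% to 12% when PCL-5 was added. That removes (22 − 12)/22 = 45% of it; a further set of runs gave roughly 40%.

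**Step 5: precision at N = 90.** When dropout is unrelated to symptoms, adding PCL-5 changes the standard error by roughly 0 to −4% (for example 0.249 to 0.239, or 0.209 to 0.210). In the 46%/26% case it rises from 0.219 to 0.228, about 4%.

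**Step 6: overall error in the 46%/26% case.** CAPS-5 only: √(0.219² + 0.07²) = 0.230. With PCL-5: √(0.228² + 0.004²) = 0.228. The gain lies in bias, not in total error. Coverage of a 95% interval from the CAPS-5-only model is about 93.8% (shift 0.07/0.219 = 0.32 standard errors).

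**The case against.** The strongest objection is that the plan does have a missing-data rule. Above 10% missing, early leavers may receive an imputed CAPS-5. A reader might infer from the schedule that they contribute nothing to the Hypothesis 2 result, or that the planned estimate is 20% too small. The documents support neither: at the dropout rates that produce 20%, imputation would be triggered, so the unimputed CAPS-5-only model is not the planned analysis. This stands, and the figures above are not the error of the planned analysis. What remains is that the rule names no predictors. PCL-5 is neither required nor excluded, so the result depends on a choice still open.

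Below 10% the plan does nothing, and there the bias is small: under 1% with the same mechanism in both arms, about 5% with placebo-only dropout near 10%. That also stands, although 5% is not the absence of bias under any mechanism that the plan asserts.

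A reader might also infer that PCL-5 would remove the bias altogether. It did so in simulation because dropout was generated from recorded PCL-5; under unrecorded severity it removed less than half. Nor does the point extend to people who merely stop medication: Table 1 still schedules CAPS-5 at week 8 and follow-up, and nothing says that stopping treatment ends assessment.

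Finally, a baseline-adjusted mixed model on CAPS-5 is conventional and valid if dropout depends only on what it conditions on. The placebo-only scenarios bias toward no effect, and total error barely changes. These are fair reasons to call this an improvement rather than a fatal flaw.

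**Conclusion.** The point holds in limited form. The Hypothesis 2 model uses CAPS-5 alone, on-treatment CAPS-5 exists only at weeks 4 and 8, and no text commits the analyst to using the weekly PCL-5 when CAPS-5 is missing.

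Under assumed dropout, a CAPS-5-only likelihood analysis is understated by about 0–4% if symptom-related dropout works alike in both arms. If it is confined to placebo, the understatement is roughly 5% with placebo dropout near 10%, rising to 20% or more near 40%. The larger figures need dropout that is both symptom-related and different by arm, and no document establishes either. The size of any bias under the plan's own imputation cannot be stated, because that imputation is not specified.

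The case for change rests on protection against a plausible bias at almost no cost, using data already scheduled. It does not rest on precision, where the gain is negligible. The change is worth making before unblinding.

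**What to change.** Keep CAPS-5 as the Hypothesis 2 outcome. For this hypothesis, replace the 10% rule with one prespecified method, applied to all randomised participants whatever the percentage missing. Either of these would do:

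- multiple imputation of CAPS-5 using arm, baseline and week-4 CAPS-5, and baseline and weekly PCL-5; or
- a joint CAPS-5/PCL-5 mixed model with the same variables.

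At N = 90 the weekly PCL-5 scores may need to be summarised to limit the number of parameters; if so, fix the summary in advance. Keep the CAPS-5-only model as a sensitivity analysis. Add a missing-not-at-random analysis, since PCL-5 cannot fully correct for dropout driven by unrecorded symptoms. Remove, for this hypothesis, the statement that small amounts of missing data cannot bias the result.

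Cost: a little more analysis work and wording, and a slightly larger standard error in some dropout patterns (0.219 to 0.228 in the case above). No new data, visits or change of endpoint.
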